1.2. Exploratory Aims

- Secondary urinary outcomes:** To compare treatment with Botox A to treatment with mid-urethral sling for improving the number of urinary incontinence episodes on bladder diary 6 months post-treatment.
- Predictors of poor treatment response:** To develop models to identify baseline predictors of change of MUI, OAB, and SUI outcomes measured using the UDI, between baseline and 6 months post-treatment.
- Quality of life and global impression:** To compare quality of life outcomes and Patient Global Impression-Improvement (PGI-I), Patient Global Impression-Severity (PGI-S) between groups randomized to Botox A versus mid-urethral sling 6 months post-treatment.
- Safety and additional treatments:** To describe rates of reoperation (sling revision) after mid-urethral sling and intermittent catheterization due to voiding dysfunction/partial urinary retention after Botox A detrusor injection, to compare the proportion of women in each group with UTI and recurrent UTI, rates of other serious and non-serious adverse events, and to compare the proportion of women in each group initiating additional (off protocol) treatment other than Botox A and mid-urethral sling for SUI and/or OAB.
- Cost-effectiveness analysis:** To determine the cost effectiveness of Botox A injection versus mid-urethral sling for the treatment of MUI symptoms on an intent-to-treat basis 6 months post-treatment.
- UDI MID:** To explore MIDs for UDI total score and stress and irritative subscores for this MUI population.

[figure not shown]

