3.1.2 Exploratory Aims

Exploratory aims of this study (consolidated from the main protocol and the 12-month addendum) are the following:

- 1. **12-month aim:** To compare the effectiveness of intradetrusor injection of 100 units of Botox A to mid-urethral sling for change in MUI symptoms 12 months following treatment
- 2. Secondary urinary outcomes: To compare treatment with Botox A to treatment with mid-urethral sling for improving the number of urinary incontinence episodes on bladder diary 6 and 12 months post-treatment.
- 3. **Predictors of poor treatment response:** To develop models to identify baseline predictors of change of MUI, OAB, and SUI outcomes measured using the UDI, between baseline and 6 and 12 months post-treatment.
- 4. **Quality of life and global impression:** To compare quality of life outcomes and Patient Global Impression-Improvement (PGI-I), Patient Global Impression-Severity (PGI-S) between groups randomized to Botox A versus mid-urethral sling 6 and 12 months post-treatment.
- 5. **Safety and additional treatments:** To describe rates of reoperation (sling revision) after mid-urethral sling and intermittent catheterization due to voiding dysfunction/partial urinary retention after Botox A detrusor injection, to compare the proportion of women in each group with UTI and recurrent UTI, rates of other serious and non-serious adverse events, and to compare the proportion of women in each group initiating additional (off protocol) treatment other than Botox A and mid-urethral sling for SUI and/or OAB.
- 6. **Cost-effectiveness analysis:** To determine the cost effectiveness of Botox A injection versus mid-urethral sling for the treatment of MUI symptoms on an intent-to-treat basis 6 and 12 months post-treatment.
- 7. **UDI MID:** To explore MIDs for UDI total score and stress and irritative subscores for this MUI population.

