9.5.2 Cost-effectiveness analysis

The EQ-5D and the SF-6D will be used to calculate QALYs. Methods for cost-effectiveness analysis from the protocol are included here and will be expanded upon is a cost-effectiveness analysis SAP that will be developed prior to analysis of the cost effectiveness data, which will be reported in a secondary manuscript.

Differential mean costs and differential mean QALYs between the two treatment groups will be estimated using multiple regression analysis. Specifically, a generalized linear model with appropriate link function (e.g., log-link) and response probability distribution (e.g., gamma distribution) will be used to analyze costs due to the potential skewness and heteroscedasticity of medical expenditure data, while an ordinary least squares regression will be used for analyzing QALY data. The models will account for stratification factors of study site and age group, as well as other characteristics of the subjects that are found to differ significantly between the groups. When estimating QALYs, we will also adjust for subjects' baseline utility scores to account for potential imbalance in baseline utility between the two treatment groups.

We will calculate the incremental cost-effectiveness ratio (ICER), which is the differential mean costs divided by the differential mean QALYs between the two groups, to assess the additional costs associated with each additional QALY gained. Our base case analysis will be conducted based on subjects with complete data. Sensitivity analysis will be conducted to include subjects with incomplete data using the multiple imputation method. Non-parametric bootstrapping resampling technique will be used to derive the 95% confidence interval for the ICER. In addition, cost-effectiveness acceptability curve (CEAC) will be generated to illustrate the likelihood that one treatment is more cost-effective than the other with various ceiling cost-effectiveness ratios.

We plan to conduct supplemental analyses using alternative outcome measures, such as incremental cost per reduction in UIE/day.

The cost-effectiveness evaluations will be conducted as within-trial comparisons. A decision analytic model will also be developed from trial data to evaluate the trajectory of the cost-effectiveness ratio.

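### The cost-effectiveness aim is stated as intent-to-treat, but its base case keeps only women with complete data, puts a bootstrap interval on the ICER and lets significance choose covariates

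*SAP*

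**What the plan says.** **Aim.** Protocol 1.2 sets out to determine cost-effectiveness "for the treatment of MUI symptoms on an intent-to-treat basis 6 months post-treatment". The addendum's background repeats this, and SAP 3.1.2 extends it to 12 months ("on an intent-to-treat basis 6 and 12 months post-treatment").

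**Base case.** SAP 9.5.2, Protocol 6.2.3 item 5 and item 5 of the addendum's analysis plan all carry the same sentence: "Our base case analysis will be conducted based on subjects with complete data". None of them defines what makes a woman's data complete.

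**Missing data.** "Sensitivity analysis will be conducted to include subjects with incomplete data using the multiple imputation method".

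**Uncertainty.** "Non-parametric bootstrapping resampling technique will be used to derive the 95% confidence interval for the ICER". In addition, a "cost-effectiveness acceptability curve (CEAC) will be generated to illustrate the likelihood that one treatment is more cost-effective than the other".

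**Covariates.** The models adjust for site and age group, "as well as other characteristics of the subjects that are found to differ significantly between the groups". The QALY model also adjusts for baseline utility.

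**Status.** The aim is exploratory. SAP 2 and 9.5.2 say that a separate cost-effectiveness SAP will expand on these methods before the data are analysed, and that the results go to a secondary manuscript.

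**The concern.** A QALY total needs a utility at every scheduled visit, and a cost total needs every cost form. Under a complete-data rule one missing form removes the woman and everything she did report. The result then describes a subset selected after randomization, although the aim calls for an intent-to-treat comparison. If women who do badly, or well, in one arm are the ones who miss forms, the difference is biased.

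Two weaknesses sit beside this. A percentile interval for a ratio stops being readable when its denominator can be zero or change sign. And a between-arm significance test is a poor way to choose covariates in a randomized trial, because it makes the model depend on chance imbalance.

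At stake is the main result of the cost-effectiveness manuscript, not the primary UDI comparison.

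**Working it through.** The documents give no cost, QALY or sample-size figure for this analysis, so there is no planned figure to reproduce. The only relevant planned quantities are the 146 women randomized, 5% discontinuation by 6 months and a further 5% by 12 months (SAP 6). These leave 146 × 0.95 = 138.7 and 146 × 0.90 = 131.4 women.

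**1. Populations side by side.**
- Aim: intent-to-treat (Protocol 1.2, SAP 3.1.2).
- Default for efficacy outcomes: mITT, meaning treated with some post-baseline efficacy data (SAP 5.1). SAP 3.2.3 lists cost-effectiveness among the exploratory efficacy outcomes.
- Base case: complete data (SAP 9.5.2).

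These are three different sets for one result. By contrast, the primary UDI model uses all available repeated measures under missing at random (SAP 7.3, 9.3).

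**2. Number of forms.** Protocol 3.4.3.d collects utilities at baseline, 3 and 6 months: three assessments. The SAP 4.6 flow chart, as far as the table can be read, adds 2 weeks, 9 and 12 months: six assessments. Timing of the cost questionnaire differs within Protocol 3.4.3.d (2 weeks and 6 months, or 3 and 6 months) and again in SAP 4.6. Two women did not consent beyond 6 months (SAP 1), so they cannot be complete at 12 months.

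**3. Illustrative loss.** Assume each assessment is 95-97% complete, independently.

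| Horizon | Complete | Dropped | Planned loss |
|---|---|---|---|
| 6 months, 3 assessments | 0.95³ = 0.857 to 0.97³ = 0.913 | 9-14% | 5% |
| 12 months, 6 assessments | 0.95⁶ = 0.735 to 0.97⁶ = 0.833 | 17-26% | about 10% |

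Independence drives these figures. If the same women missed every form, the loss at these rates would be only 3-5%.

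A second illustration takes the planned discontinuation first and then lets each follow-up form be missing independently in 3-10% of women:
- 6 months, two forms: 146 × 0.95 × 0.97² = 130.5, down to 146 × 0.95 × 0.90² = 112.3.
- 12 months, four forms: 146 × 0.90 × 0.97⁴ = 116.3, down to 146 × 0.90 × 0.90⁴ = 86.2.

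**4. Can complete cases mislead?** With utilities u0, u3 and u6, the 6-month QALY is 0.25 × [(u0 + u3)/2 + (u3 + u6)/2], so a missing u6 discards an observed u3. A deliberately adverse simulation (73 per arm) let missingness of u6 depend on u3 in opposite directions in the two arms. The adjusted full-data difference was about 0.0095 QALY.
- With 5-7% missing, complete cases gave 0.011 to 0.013.
- With 20-22% missing, they gave 0.016 to 0.022.
- Regression imputation using u3 returned about 0.0095, as it should when missingness depends only on u3.

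This shows that bias is possible. It does not estimate its size in this trial.

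**5. The ICER interval.** A utility gap of 0.05 sustained for 6 months gives at most 0.05 × 0.5 = 0.025 QALY. With 69 per arm and an assumed QALY SD of 0.05 to 0.10, the 95% half-width is 1.96 × SD × √(2/69), or 0.017 to 0.033. For true differences of 0.005 to 0.03, the chance that the interval for the QALY difference includes zero runs from 6% (difference 0.03, SD 0.05) to 94% (difference 0.005, SD 0.10).

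Bootstrap examples, assuming QALY SD 0.075 and a cost difference and cost SD of 1,500 each:

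| QALY difference | Replicates below zero | Percentile ICER interval |
|---|---|---|
| 0.01 | 21% | about -821,000 to +833,000 |
| 0.04 | 0.04% | about 17,700 to 84,200 |

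The first interval cannot be read as a range from better to worse value, because negative ratios mix replicates that are cheaper and better with replicates that are dearer and worse. The second is usable.

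**6. Covariates.** SAP 7.8 makes p-values for baseline characteristics descriptive only. For the primary outcome, SAP 7.2 confines adjustment for observed imbalances to supportive exploratory analyses. SAP 9.5.2 puts covariates selected by significance into the main cost and QALY models.

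**The case against.** The other side has real weight.

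- **Not the last word.** The aim is exploratory and a dedicated SAP is still to come. This stands and limits the severity. But that document is described as expanding the methods given here, so the complete-data default carries forward unless someone changes it.
- **Remedies already planned.** Multiple imputation will show whether the base case holds, and the acceptability curve remains readable when the QALY difference is near zero. This also stands in part. A curve built on complete cases inherits their selection, however, and it does not repair the ratio interval reported beside it.
- **Intent-to-treat may refer to grouping only.** SAP 7.4 uses the term for keeping data after cross-over. On that reading the aim does not settle how missing forms are handled, and the conflict is partly one of definition. Even so, randomized women are dropped and the population is left unnamed.

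A reader might infer that the base case is valid only if data are missing completely at random. That goes too far: these are regressions on arm, site and age group, with baseline utility in the QALY model, and they tolerate missingness that depends on those terms. The exposure is to missingness that depends on follow-up outcomes.

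A reader might also infer that the QALY difference should be expected to straddle zero. The documents give neither a difference nor an SD, and the 6% to 94% range shows that the answer rests on the assumptions.

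**Conclusion.** The point holds as a moderate one. The stated aim and the base case do not match, a better analysis is already in the plan but ranked second, the ICER interval may be unreadable, and the covariate rule contradicts the SAP's own treatment of baseline p-values.

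Its size cannot be fixed from the documents. The losses of 9-14% at 6 months and 17-26% at 12 months rest on assumed 95-97% completeness and on independence. Clustering of missed forms within women would reduce them. It would be wrong to set the 26% against the planned 5%: the 26% is a 12-month count and belongs beside about 10%. The bias and interval examples likewise rest on assumed utilities, SDs and costs. Nothing here touches the primary UDI analysis, its sample size or its conclusions.

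**What to change.** Carry three changes into the cost-effectiveness SAP before those data are analysed.

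1. **Base case.** Make the multiply imputed analysis, with women compared by randomized arm, the base case, and complete cases the sensitivity analysis. Name the population: either all randomized women, or mITT with the aim reworded to match. Define which utility and cost forms make a woman complete, and reconcile the cost-questionnaire timing in Protocol 3.4.3.d and SAP 4.6.
2. **Uncertainty.** Report incremental costs, incremental QALYs and incremental net monetary benefit at stated thresholds, each with a bootstrap 95% interval that also reflects the imputation. Show these beside the planned acceptability curve, in place of the ICER interval. The ICER can stay as a point estimate.
3. **Covariates.** Adjust for site, age group and, for QALYs, baseline utility. Drop covariates selected by between-arm significance.

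The cost is small: two planned analyses change places and a few summaries are added, with no new data collection. The downside is that the base case then relies on the imputation model, so that model should be specified in advance and the complete-case result shown next to it.

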9.5.3 UDI MID

We will explore potential minimally important differences (MIDs), the smallest change that can be regarded as clinically meaningful, for UDI total score and stress and irritative subscores for this MUI population.

MIDs will be calculated using anchor- and distribution-based approaches. Potential anchors include the PGSC, patient global impression of improvement (PGI-I), and incontinence episodes from the bladder diary.

Anchor-based methods will examine the relationship between the UDI scores and independent external measure (or anchor) to elucidate the meaning of a particular change in the score. The anchor-based MID approach will evaluate the change from baseline at 6 months in the UDI score and 2 subscores corresponding to a self-reported small, but important, change on the PGSC, PGI-I and number of incontinence episodes from the diary.

- The PGSC "My current treatment is giving me adequate control of my urine leakage" is scored on a scale from 1 (strongly disagree) to 5 (strongly agree). Responses of 1, 2, or 3 are considered inadequate leakage control, responses of 4 or 5 are considered adequate leakage control. The MID will be defined as the difference between the mean change in UDI scores for patients whose PGSC rating at 6 months was "4" and the mean change in UDI scores for patients whose PGSC rating at 6 months was "3.
- The PGI-I "the one that best describes how your urinary tract condition is now, compared with how it was before treatment in this study" is scored on a scale from Very much better, Much better, A little better, No change, A little worse, Much worse, Very much worse. . The MID will be defined as the difference between the mean change in UDI scores for patients whose PGI-I rating at 6 months was "a little better" and the mean change in UDI scores for patients whose PGI-I rating at 6 months was "no change".
- Change in average incontinence episodes per day from baseline to 6 months will be calculated from the 3-day diary. "No change" in episodes will be defined for a person as a percent change in average episodes across the 3 days of **from 0 to 25%**. A "small improvement" in average episodes will range from **25% to 50%**. The MID will be defined as the difference between the mean change in UDI scores for patients with a small improvement and the mean change in UDI scores for patients with no change.

Distribution-based MID calculations will focus on variability, using the baseline standard deviation of the UDI scores. The distribution-based MID will be defined as $0.5 \times$ baseline SD (i.e., medium effect size) and $0.2 \times$ baseline SD (i.e., small effect size).

MID estimates of the anchor- and distribution-based approaches will be compared, and recommendations for the MID of the UDI and iterative and stress subscales will be made by consensus, consistent with the recommendations of Revicki et al. For reference, ESTEEM used the anchor-based method and the PGI-I (selected as the most clinically relevant anchor), and recommends a MID of -26 for the UDI total, -10.2 for the UDI-irritative subscale, and - 5.4 for the UDI-stress subscale.(Sung et al)

The change from baseline UDI total score and stress and irritative subscores for each participant will be compared to the MIDs estimated from the MUSA data, and the percentage of participants who meet or exceed the MID will be compared between treatment groups.

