6.2.2 Primary Aim

Primary Outcome

The mean change from baseline in UDI total score will be compared between groups at 6 months at the $p<0.05$ statistical significance level using a mixed effects analysis of covariance model for repeated measures (MMRM) with adjustment for baseline UDI score, and randomization stratification factors site and age group. The model will include fixed effect categorical factors for treatment group, visit (3 and 6 months), and treatment \times visit interaction with a heterogeneous Toeplitz covariance pattern for the within-subject repeated measures. Estimates, p-values and 95% confidence intervals will be presented for treatment group comparisons at 6 months (primary) and 3 months (secondary).

This model assumes missing data due to a missed visit or early study discontinuation is missing at random. If more than 10% of participants are missing their 6-month score, then a sensitivity analysis will be performed using multiple imputation under a variety of missing data patterns to be specified in the statistical analysis plan in order to assess the robustness of the primary results to missing data. .

We will report whether change in total UDI score from baseline to 6 months is statistically significantly different between groups. If the difference is statistically significant, the potential clinical significance of the difference will be discussed. We recognize that our sample size may allow us to find a difference between groups that is statistically significant yet smaller than published MID for total UDI score for women with MUI. However, published MIDs were calculated based on populations that may be somewhat different from the one targeted for enrollment in MUSA, and an exploratory aim of MUSA is to explore whether the MID in this population differs from previously published values.

Secondary Outcomes

There are two secondary outcomes for the primary aim. The mean change from baseline in UDI-stress and UDI-irritative subscores will be compared between groups at 6 months. Each of these outcomes will be evaluated using an alpha level of 0.05, with no adjustment for multiple comparisons. The statistical analysis of the two secondary outcomes will be identical to the analysis described above for the UDI total score.

6.2.3 *Exploratory Aims*

All statistical evaluations of the exploratory aims are for descriptive purposes and p-values resulting from these analyses will not be evaluated for statistical significance.

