Change from baseline in Urge Incontinence Episodes at 6 months (and at 3 and 12 months)	Continuous	The daily frequency of urge incontinence episodes will be taken from the bladder diary. The outcome will then be computed as the difference in daily frequency of urge incontinence episodes at 6 months (and 3 and 12 months) and the daily frequency of urge incontinence episodes at baseline. If data for the assessment time point are missing, the outcome variable will be coded as missing.
Change from baseline in Stress Incontinence Episodes at 6 months (and at 3 and 12 months)	Continuous	The daily frequency of stress incontinence episodes will be taken from the bladder diary. The outcome will then be computed as the difference in daily frequency of stress incontinence episodes at 6 months (and 3 and 12 months) and the daily frequency of stress incontinence episodes at baseline. If data for the assessment time point are missing, the outcome variable will be coded as missing.
Change from baseline in Mixed or Don't Know Incontinence Episodes at 6 months (and at 3 and 12 months)	Continuous	The daily frequency of mixed urge and stress incontinence episodes will be taken from the bladder diary. The outcome will then be computed as the difference in daily frequency of mixed incontinence (noted on diary as "both stress/urge") or "don't know" episodes at 6 months (and 3 and 12 months) and the daily frequency of mixed incontinence episodes at baseline. If data for the assessment time point are missing, the outcome variable will be coded as missing.
Change from baseline in Total Incontinence Episodes at 6 months (and at 3 and 12 months)	Continuous	The daily frequency of total incontinence episodes will be taken from the bladder diary. The outcome will then be computed as the difference in daily frequency of total incontinence episodes at 6 months (and 3 and 12 months) and the daily frequency of total incontinence episodes at baseline. If data for the assessment time point are missing, the outcome variable will be coded as missing.

Variable	Туре	Definition				

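### The diary anchor's no-change band in SAP 9.5.3 has no sign and shares its 25% limit with small improvement; read as a reduction, it is one-sided and gives a smaller diary MID than a two-sided band would

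*SAP*

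**What the plan says.** SAP 9.5.3 lists three potential anchors for the UDI MID: the PGSC, the PGI-I and incontinence episodes on the 3-day diary. For the diary, no change "in episodes will be defined for a person as a percent change in average episodes across the 3 days of" 0 to 25%, while 25% to 50% counts as a small improvement. The estimate is a contrast of these two groups: "The MID will be defined as the difference between the mean change in UDI scores for patients with a small improvement", set against women in the no-change group.

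The section does not say whether the percent change is a reduction, an increase or an absolute value. It does not assign a value of exactly 25% to one group, and it names no group for women who get slightly worse. SAP 9.2 does give a sign for the diary outcome itself ("The outcome will then be computed as the difference in daily frequency of total incontinence episodes at 6 months" minus baseline), but that is a difference in daily frequency, not a percent change.

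The PGI-I anchor in the same section compares 'a little better' with 'no change' on a scale that runs "Very much better, Much better, A little better, No change, A little worse, Much worse, Very much worse".

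Anchor-based and distribution-based estimates are then compared, and "recommendations for the MID of the UDI and iterative and stress subscales will be made by consensus". After that, "the percentage of participants who meet or exceed the MID will be compared between treatment groups". SAP 9.5.1 uses the same MID to define success in the prediction work.

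**The concern.** An anchor-based MID is the UDI change in women who improved a little, less the UDI change in women who did not change. If the reference group leans towards improvement, part of the signal is subtracted away. The PGI-I anchor avoids this, because its no-change category has slight improvement on one side and slight worsening on the other. The diary band, read as a reduction, starts at zero and extends only towards improvement.

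The missing sign is a second problem. A programmer has to guess a direction, and the guess changes the estimate. The diary value is one input to the recommended MID, which sets the threshold for the responder comparison. SAP 9.3 also points to 9.5.3 when it describes how the clinical significance of a primary difference will be discussed. SAP section 6 suggests that the trial may help show whether the true MID is below 26, and on the natural reading the one-sided band pushes the diary estimate in that same direction.

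**Working it through.** The SAP states no diary MID, so there is no figure to reproduce. The check compares how far apart the two groups lie on the diary scale under each reading. If UDI change is linear in percent diary change, the diary MID is proportional to that distance and the slope cancels in a ratio.

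**Definition.** Percent reduction = 100 × (baseline − 6 months) / baseline, so improvement is positive.

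**Even spread of reductions.** Small improvement (25% to 50%) has mean 37.5.
- Reduction reading (0 to 25%): reference mean 12.5; separation 37.5 − 12.5 = 25.
- Two-sided band (−25% to 25%): reference mean 0; separation 37.5.
- Increase reading (−25% to 0 on this scale): reference mean −12.5; separation 37.5 + 12.5 = 50.
- Absolute-value reading: the same as the two-sided band apart from its end points.

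Ratios to the two-sided band: 25 / 37.5 = 0.67 for a reduction and 50 / 37.5 = 1.33 for an increase.

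**Simulated integer diaries.** Protocol 4.1.1 gives 6.6 total episodes per day for the ESTEEM women with at least 4 urgency episodes, so 6.6 × 3 = 19.8, about 20 per 3-day diary. The other inputs are assumptions.

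1. Women at exactly 25% placed only in small improvement. Baseline counts are negative binomial with a minimum of 4 (resulting mean 3.2 to 6.9 per day), follow-up is Poisson, and mean improvement is 20% to 70%. The as-written reference group averages about 10% to 12% improvement; the two-sided group averages about 1% to 4%. Separation is 27 to 31 points against 35 to 38, a ratio of 0.76 to 0.80. The increase reading gives 1.28 to 1.38.
2. Both limits inclusive as written, against the bands proposed under the fix. Baseline mean is 12 or 20 per diary (minimum 4), and follow-up is Poisson around a lognormal individual ratio with median 0.45 or 0.60 and log SD 0.7 or 0.9. Separation is 26 to 27 points against 32 to 34, a ratio of 0.77 to 0.83.

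Across the even spread and both simulations the reduction reading gives ratios of 0.67 to 0.83, so the shortfall is 1 − 0.83 = 17% to 1 − 0.67 = 33%. A tighter spread of response would bring the ratio nearer to 1, so this range illustrates the size and does not bound it.

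**Group sizes.** Among 2 × 69 = 138 evaluable women, the first simulation puts 5 to 24 in the one-sided reference group and 7 to 36 in the two-sided one.

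**Exactly 25%.** With at least 4 urgency episodes required at entry, changes such as 4 to 3, 8 to 6 or 12 to 9 are attainable. In the first simulation these women are about 3% to 7% of those in the 0 to 50% range. Moving them from one group to the other shifts the separation by 0.3 to 1.1 points.

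**The case against.** The strongest reply is that the text fixes no direction. An absolute-value reading is already two-sided, and an increase reading makes the MID larger, so a reader who infers that the diary MID simply comes out too small goes beyond the SAP. This stands: the shortfall is conditional on the reduction reading. That reading is nonetheless the natural one. The neighbouring band is labelled an improvement, and under the increase reading the two bands would run in opposite directions and leave women with reductions below 25% in neither group.

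A reader might also infer that the reference group consists of improved women. It does not. The band includes zero, and 20% to 38% of the group had exactly no change in the first simulation. Treating a change below a quarter on a 3-day diary as unimportant is a defensible choice; the question is why it should apply in one direction only.

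It would be tempting to blame the overlap at 25% for the shrinkage, or to scale the ESTEEM value of −26 by the ratios above. Neither is supported. The overlap is a separate and small ambiguity, and −26 was anchored on the PGI-I. The documents contain no diary-anchored MID to scale.

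Finally, the consequence is limited. The diary is one of several inputs to a consensus, the SAP records that ESTEEM judged the PGI-I the most clinically relevant anchor, and Protocol 6.2.3 says "All statistical evaluations of the exploratory aims are for descriptive purposes". That stands, and it makes this a minor point.

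**Conclusion.** The definition needs correcting. As written it has no sign and places women at exactly 25% in both groups. On the natural reading it also keeps slight improvers in the reference group while leaving slight worseners out. That makes the diary MID smaller than a two-sided band would. The direction follows if UDI improvement rises with diary improvement. The size, about 17% to 33%, rests on linearity and on assumed diary distributions, with no UDI-by-diary data in the documents to test either. The increase reading would give a larger MID (ratio 1.28 to 1.38) and the absolute-value reading no bias, so the estimate depends on a coding choice that the SAP leaves open.

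The reach is one exploratory anchor estimate and, through the consensus MID, the responder percentages and the success definitions. How far a low diary value would move the consensus cannot be determined from the documents. The primary test and the sample size do not use it.

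**What to change.** In SAP 9.5.3, define percent reduction = 100 × (baseline − 6 months) / baseline, using average daily episodes. Then state:
- no change: more than −25% and less than 25%;
- small improvement: at least 25% and less than 50%;
- all other women: in neither group.

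If an absolute-value reading was intended, this only records it. The cost is two lines of text and the matching code. The one consequence to accept is that women with up to nearly 25% more episodes join the reference group. This widens the contrast and, in the simulations, enlarges the group. If the sponsor prefers a one-sided band, the SAP should say so, with the sign and the reason, so that readers can interpret the smaller MID.
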